5 EFFICACY

The study is not designed to detect significant changes in cognition over time. However, using available data from analysis of the secondary endpoints, including changes in cognition scores from baseline, descriptive summarization as well as appropriate 95% confidence limits will be developed. Of particular interest will be the within-subject changes from baseline and their distribution around a null value of zero and a comparison among groups to evaluate any trends in dose response. For each efficacy endpoint, paired t-test may be conducted to evaluate within-subject changes from baseline. Between-group differences may be assessed by Analysis of Covariance (ANCOVA) including baseline and sex as the covariates. Between-group difference may be assessed by analysis of Covariance (ANCOA) including baseline and sex as the covariates. Figures, including line graphs or bar graphs, may be generated to show treatment group differences on selected endpoints.

For analysis purposes, results at early termination visits will not be included in tabulated summaries.

Following efficacy endpoints will be analyzed based on both EVAL and PPROT sets.

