10.3 ANALYSIS DATASETS

Four analysis datasets are possible however, analyses may not necessarily be conducted with all four:

- **Intention-to-Treat (ITT) Dataset:** all randomized participants.
- **Safety Dataset:** all subjects who received at least one dose of the study agent.
- **Evaluable Dataset:** all subjects who receive at least 5 of the 10 planned doses.
 - **Per Protocol Dataset:** a subset of the Evaluable Dataset comprised of subjects who have no Major Protocol Deviations.

The presentation of baseline characteristics will be conducted on the ITT dataset. All safety analyses will be performed for the Safety Dataset. Analyses of the secondary endpoints will focus on the Evaluable and/or Per Protocol Datasets.

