2.4 Analysis Sets

- Screened set (SCRN): All subjects who were screened and entered into EDC.
- Screen Failure set (SCRf): All subjects who were entered as screen failures in the EDC.
- Intention-to-Treat Dataset (ITT): All subjects who were randomized.
- Safety set (SAF): All subjects who received at least one dose of the study agent.
- Evaluable set (EVAL): All subjects who received at least 5 of the 10 planned doses.
- Per Protocol set (PPROT): A subset of the Evaluable set comprised of subjects who do not have any of the deviations listed below or any other deviation affecting efficacy identified prior to database lock.

Deviation Type	Deviation	Additional Clarification
Eligibility Inclusion Criteria Not Met	Diagnosis of probable AD based upon the National Institute on Aging-Alzheimer's Association (NIA-AA) Criteria	Subjects with a clinical diagnosis of AD according to NIA-AA criteria who have a negative amyloid PET scan will also be excluded.
Eligibility Inclusion Criteria Not Met	MMSE Score 12-24 inclusive	
Eligibility Inclusion Criteria Not Met	Modified Hachinski Ischemia Scale (MHIS) score of ≤ 4	
Eligibility Exclusion Criteria Met	Evidence of clinically relevant neurological disorder(s) other than AD	
Eligibility Exclusion Criteria Met	Initiation or change in the dosage of cholinesterase inhibitors (AChEI), memantine, Axona, vitamin E supplementation, or selegiline within 3 months prior to screening	Will be determined based upon actual date of change and proximity to screening. Will be determined prior to database lock
Eligibility Exclusion Criteria Met	Treatment with any human blood product, including transfusions and IV immunoglobulin, during the 6 months prior to screening	
Eligibility Exclusion Criteria Met	Concurrent daily treatment with benzodiazepines, long-acting opioids, or other medications that, in the investigator's opinion, interfere with cognition	
Eligibility Exclusion Criteria Met	Concurrent participation in another interventional clinical trial. Prior clinical trial subjects must have been off study agents for at least 30 days (or 5 half-lives, whichever is longer), 4 months for disease modifying therapies, and 1 year for vaccine or immunotherapy trials prior to screening.	

Deviation Type	Deviation	Additional Clarification

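### Every efficacy table and any between-dose ANCOVA uses only sets that exclude, after randomisation, subjects with fewer than 5 of the 10 doses, so an apparent dose trend could be a selection effect

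*SAP*

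**What the plan says.** SAP section 5 fixes the populations for efficacy: "Following efficacy endpoints will be analyzed based on both EVAL and PPROT sets". Section 2.4 defines them. The first is "Evaluable set (EVAL): All subjects who received at least 5 of the 10 planned doses". The second is "Per Protocol set (PPROT): A subset of the Evaluable set comprised of subjects who do not have any of the deviations listed below", so it inherits the five-dose condition and adds further exclusions. Section 2.4 also defines a randomised set, "Intention-to-Treat Dataset (ITT): All subjects who were randomized".

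In the output lists (SAP sections 10 and 11), Tables 14.2.1 to 14.2.8 all carry EVAL and PPROT. For efficacy data, ITT appears only in Listings 16.2.6.1 to 16.2.6.8. The SAP follows Protocol section 10.3 here: "Analyses of the secondary endpoints will focus on the Evaluable and/or Per Protocol Datasets".

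On the comparison itself, SAP section 5 counts among its main interests "a comparison among groups to evaluate any trends in dose response", and adds: "Between-group differences may be assessed by Analysis of Covariance (ANCOVA) including baseline and sex as the covariates". Section 2.2 says the between-group differences are meant to inform the design of later studies.

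Two further rules matter. SAP section 5 keeps early termination results out of the tabulated summaries, and SAP section 2 imputes nothing unless stated otherwise.

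**The concern.** Randomisation makes the two dose groups comparable at entry. Selecting on doses received can undo that if dose affects who reaches five infusions. Here the selecting variable is close to the primary question: Protocol section 4.2.1 makes the numbers completing 5 and 10 infusions the primary feasibility endpoint, and builds the tolerability endpoints on completion after those counts. The plan thus treats completion as an outcome that may differ by dose, and also uses it as the entry rule for comparing doses on cognition.

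At stake is the reading of a dose trend. If the arms lose different numbers, or different kinds of subjects, the EVAL groups are no longer the randomised groups. A later study could then take its dose from a contrast that is partly selection. No planned efficacy table would let a reader compare the EVAL result with one on the groups as randomised.

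**Working it through.** **1. The plan's own figure.** The Protocol Summary assumes 25% drop-out from about 40 subjects: 40 × (1 − 0.25) = 30 evaluable, as stated. So the plan itself allows for up to 10 of 40 falling out. Protocol sections 5.4.2 and 10.5 count a subject as evaluable after at least 5 doses and completion through Visit 8. EVAL asks only for 5 doses, so it may lose fewer than 10. No document splits the losses by dose or gives an SD for any score.

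**2. Formula.** With 20 per arm (SAP 1.3), suppose m subjects are excluded from an arm, and their mean change differs by g SD from that of the subjects kept. The full-arm mean is (1 − m/20) × kept mean + (m/20) × excluded mean. The kept mean therefore differs from the full-arm mean by (m/20) × g. With the same g in both arms, the dose difference shifts by g × (m at 250 mL − m at 100 mL)/20.

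**3. Results.** Both g and the split are assumptions. Putting more losses in the 250 mL arm is for illustration; swapping the arms reverses the sign.

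| Excluded, 100 mL / 250 mL | g = 0.5 SD | g = 1 SD |
|---|---|---|
| 5 / 5 | 0 | 0 |
| 0 / 1 | 0.025 SD | 0.05 SD |
| 0 / 2 | 0.05 SD | 0.10 SD |
| 0 / 4 | 0.10 SD | 0.20 SD |
| 3 / 7 | 0.10 SD | 0.20 SD |
| 0 / 10 (extreme) | 0.25 SD | 0.50 SD |

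The zero row needs equal g as well as equal losses. If g differs between arms, 5 / 5 also produces a shift, of (5/20) times the difference in g.

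**4. Set against precision.** The standard error of the dose difference is SD × √(1/n1 + 1/n2).
- At 20/20: √(0.05 + 0.05) = 0.316, 95% half-width 1.96 × 0.316 = 0.62 SD.
- At 20/16: √(0.05 + 0.0625) = 0.335, half-width 0.66 SD.

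A shift of 0.20 SD is then about 0.20/0.66 = 30% of the half-width. It is smaller than the random error, but more precision would not remove it.

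**5. Would another table run be enough?** Only partly. The first tabulated efficacy timepoint is Day 6 for MMSE and Day 28 for ADAS-Cog/11, CFT, CDR-SOB, ADCS-ADL23, ADCS-CGIC and NPI-Q. A subject who leaves during Days 1 to 5 will often have only an early termination assessment, which SAP section 5 keeps out. Those data are sought: Protocol section 7.3.7 asks for the end of study assessments after at least one infusion, and section 5.4.2 encourages them within 4 to 6 weeks of the last visit.

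**6. Where such a value would fall.** For a last visit on Day 3, an assessment 4 to 6 weeks later is on Day 31 to 45. The nearest ADAS-Cog/11 timepoint is Day 28 (3 to 17 days away). The nearest MMSE timepoint (Days 6, 90, 168) is Day 6, which is 25 to 39 days away. The assignment rule has to be written with this in view.

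**The case against.** The strongest reply is that this is a declared choice, consistent between protocol and SAP, in a small two-dose study without placebo. Describing subjects who received a meaningful amount of treatment is reasonable. Efficacy is secondary and unpowered, the ANCOVA is optional, p values are nominal, and the primary safety, tolerability and feasibility outputs use the Safety Set. Unequal exclusion would also be visible: Table 14.1.1 gives analysis-set counts by treatment, Table 14.1.2 gives disposition, Table 14.1.8.2 gives infusion counts, and the ITT listings show individual scores. Protocol section 10.4.1 does not limit the final analyses to those it describes.

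Most of this stands, and it lowers the priority. It does not remove the problem. The counts show how many were excluded, not how the dose difference changes, and a reader should not have to rebuild that from listings.

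Three stronger readings are tempting but unsupported:
- A reader might infer that the sets drop those who could not tolerate the first course. The five doses are counted over both courses, so four in the first and one in the second suffice. Those excluded have fewer than five for any reason, and Protocol section 5.4.1 includes noncompliance and withdrawn consent among the reasons for withdrawal.
- A reader might infer that the dose comparison is biased. The documents give no losses by dose, so bias is possible but not shown.
- A reader might infer that one more run of the tables restores the randomised comparison. It would not, for the reason in step 5, and a set that needs a post-baseline value is still not full ITT.

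**Conclusion.** The point holds as an exposure to selection, not as a demonstrated bias. Every planned efficacy table, and any between-dose ANCOVA, is conditioned on an event after randomisation that may depend on dose, and none shows the groups as randomised. The shift is zero with balanced, similar losses. It is about 0.05 to 0.20 SD if 1 to 4 of 20 are lost from one arm only with a 1 SD gap. Both the one-sided loss and the gap are assumptions, and the sign is unknown. The calculation also fixes 20 per arm, although subjects who leave before Visit 8 may be replaced (Protocol 10.5, SAP 1.3). Priority is low to moderate: no confirmatory claim depends on these tables, but the dose contrast is meant to guide later studies and the remedy is inexpensive.

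**What to change.** In SAP section 5 and Tables 14.2.1 to 14.2.8:

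1. Add a presentation by randomised dose for all randomised, dosed subjects with a baseline and at least one post-baseline value. Name it as the set for between-dose comparisons, including the ANCOVA. Subjects who are later replaced stay in it.
2. For this set, lift the exclusion of early termination results and assign each to the nearest scheduled timepoint for that endpoint. State a tie rule and show the actual study day, because for MMSE the nearest timepoint can be weeks away.
3. Report, by arm, the number randomised with no post-baseline value, since this set is close to ITT but not identical to it.
4. Keep EVAL and PPROT as supportive.

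Also reconcile Protocol section 6.1.8, which ties being evaluable in the intent-to-treat population to 5 exposure days, with Protocol section 10.3 and SAP section 2.4, where ITT is everyone randomised.

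The cost is one more population in existing tables plus a short assignment rule. The downside is that the estimate includes subjects with little exposure, so it does not describe the effect of a full course. EVAL remains available for subjects who received at least five doses.

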5.1 Mini-Mental State Examination (MMSE)

The MMSE (Folstein 1975) consists of the following 5 components:

- Orientation to time and place (2 items)
- Registration of 3 words (1 item)
- Attention and calculation (1 item)
- Recall of 3 words (1 item)
- Language (6 items)

The scores from the 5 components are summed to obtain the overall MMSE total score. The MMSE total score can range from 0 to 30, with higher scores indicating better mental status.

Although available in the raw data, the MMSE total score will be recalculated. If a subject has 1 missing item, the following algorithm will be used to compute the total score: $\text{Total score} = \left[\frac{\text{total score from completed items}}{\text{maximum total score for completed items}} \right] \times (\text{maximum total score} [=30])$ for all items in the scale). The total score is then rounded to the next highest integer. If there is more than 1 missing item, the total score will be considered missing at that time point.

Changes from baseline for the recalculated MMSE total score will be summarized at each scheduled timepoint (Days 6, 90, and 168) (Table 14.2.1).

5.2 Alzheimer's Disease Assessment Scale-Cognitive Subscale (ADAS Cog/11)

The ADAS-Cog/11 (Rosen 1984) includes 11 items assessing cognitive function:

- Word Recall: the mean of the three trials is used, rounded to 2 decimal places
- Command
- Constructional Praxis
- Naming Objects and Fingers
- Ideational Praxis
- Orientation
- Word Recognition
- Remembering Test Instructions
- Comprehension
- Word Finding Difficulty
- Spoken Language Ability

Although available in the raw data, the ADAS-Cog/11 total score is derived as a linear sum of the scores recorded for the 11 individual domains. Higher scores reflect greater cognitive impairment.

Changes from baseline for the total score as well as 11 individual domain scores and will be summarized at each scheduled timepoint (Days 28, 112, and 168) (Table 14.2.2).

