7.3.4 TREATMENT

There are two inpatient treatment periods scheduled during the trial, each with a total of 5 infusions. It is anticipated that sites will infuse subjects with 5 doses over 5 days. A “grace day” is allowed in the event of unanticipated safety or health concerns during each inpatient treatment period.

Visits 3-7 (Days 1-5) and 11-15 (Days 85*-89):

*Day 85 has a ± 7-day window. Visits 12-16 should follow consecutively.

- Perform the following procedures prior to administering study treatment:
 - Review AEs and concomitant medications
 - Obtain blood and urine samples for comprehensive laboratory panel; fasting samples preferred **(Visits 4, 6, 12, and 14 Only)**
 - Obtain samples for proteomics/epigenetics/biobanking; fasting samples preferred **(Visits 3 and 11 Only)**
 - Obtain i-STAT safety laboratory test samples and assess results before each infusion
 - Perform targeted physical exam (i.e. auscultation of heart and lungs and assessment of peripheral edema)
 - Measure and record the subject’s weight in kilograms
 - Perform 12-lead ECG **(Visit 11 Only)**
 - Ensure the subject has had an opportunity to eat a meal prior to cognitive and motor testing
 - Administer the Savonix Brief Battery
 - Perform ADAS-Cog/11 **(Visit 11 Only)**
 - Collect pre-infusion vital signs
- Administer study treatment and perform safety assessments per the Infusion Administration Manual
- Post-infusion: perform 12-lead ECG **(Visits 7 and 15 Only)**

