 1. C-SSRS
 2. MMSE
 3. Savonix Full Battery
 4. ADAS-Cog/11
- Complete MRI **(Visit 8 + 4 days Only)**
- In consenting, eligible subjects, perform final lumbar puncture (after final dosing) and obtain CSF samples for optional biomarker research **(Visit 16 or within 5 days following)**

Visit 9 (Day 28 ±7 days) and Visit 17 (Day 112 ±7 days)

- Review AEs and concomitant medications
- Collect the following:
 - Vital signs
 - Blood samples for interim safety labs (Note: Subjects randomized prior to August 30, 2018, will not participate in the additional interim safety labs at Visit 9 and Visit 17.)
 - Samples for proteomics/epigenetics/biobanking (fasting samples preferred)
- Ensure the subject has had an opportunity to eat a meal prior to cognitive and motor testing
- Perform cognitive and motor testing in the following order unless otherwise specified:
 1. Savonix Full Battery
 2. ADAS-Cog/11
 3. Grooved Pegboard

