 1. MMSE
 2. Savonix Full Battery
 3. ADAS-Cog/11
 4. Grooved Pegboard

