2.3 Study Phase, Visit, and Day

The study is set up as shown above, along with assigned study period, visit, and day. In general, the baseline is defined as the last assessment before the first intake of the study medication unless otherwise specified. All scheduled assessments after first administration of study drug will be used.

Repeat/unscheduled assessments will not be used in descriptive statistics or any per-time point analyses but will be shown in listings as applicable. Pre-dose unscheduled assessments will be taken into account for baseline determination and post first dose unscheduled assessments will be taken into account for worst-case determination as applicable.

Reference date refers to the start date of the first study drug administration. All efficacy and safety assessments at all visits will be assigned a day relative to this date. The relative day will be defined as: visit date – reference date + 1 for visits on or after the reference date and visit date – reference date for visits before the reference date. Consequently, there is no 'Day 0' defined.

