2.6 Descriptive Summaries

All tabulated summaries will include the two treatment groups [REDACTED] and overall (includes data from both treatment groups). For endpoints that are continuous in nature: number of observations, mean, median, minimum and maximum, and standard deviation (SD) values will be presented as descriptive summary. For endpoints that are categorical in nature: frequency counts and percentages will be presented in the descriptive summary.

The number of decimal places to display for calculated data will be determined by the original scale of the data. Means, medians, and confidence intervals will be reported with one (1) additional decimal place. Standard deviation will be reported with two (2) additional decimal places. Minimum and maximum will be reported with the same number of significant digits as the method of capture.

For all efficacy and safety tables summarizing change from baseline, the baseline and post-baseline results at all planned timepoints will be included.

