5.3 Grooved Pegboard Test (GPT)

The Grooved Pegboard Test is a manual dexterity test measuring visual-motor coordination (Lafayette 2002). The test consists of a pegboard with 25 holes with randomly positioned slots and pegs with a key along one side. The subject is to insert the pegs as quickly as possible into the slots in sequence, first with the dominant hand and then with the non-dominant hand. The score is the time it takes for the subject to complete the task with each hand. For subjects who fail to complete the test in 5 minutes the score is the number of total pegs inserted. In addition, to time to completion, the number of pegs dropped (for each hand) is recorded.

Changes from baseline for these GPT scores will be summarized for each hand (dominant and non-dominant) at each scheduled timepoint (Days 6, 28, 85, 90, 112, and 168) (Table 14.2.3).

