5.6 Alzheimer's Disease Cooperative Study – Activities of Daily Living 23 (ADCS-ADL23)

The ADCS-ADL is an inventory of informant-based items used to assess activities of daily living and instrumental activities of daily living, (i.e., functional performance) for AD subjects (Galasko 1997). The interviewer asks the subject's caregiver a total of 23 questions regarding the subject's ability to maintain good hygiene, use a telephone, initiate conversations, etc. A score of up to 4 points may be assigned to each question. A higher score indicates less impairment; the maximum achievable score (indicating no ADL impairment) is 78. The sum of the responses for the 23 items of the inventory will be calculated for the total score and recorded into eCRF.

Changes from baseline for ADCS-ADL23 total score will be summarized for subject and trial partner separately, and at each scheduled timepoint (Days 28, 56, 112, 140, and 168) (Table 14.2.6.1 and 14.2.6.2).

5.7 Alzheimer's Disease Cooperative Study – Clinical Global Impression of Change rating (ADCS-CGIC)

The ADCS-CGIC is a process for obtaining an assessment of meaningful clinical change over time (Schneider 1997). It is a systematic method for assessing clinically significant change in a clinical trial as viewed by an independent skilled and experienced clinician. The ADCS-CGIC focuses on clinicians' observations of change in the subject's cognitive, functional and behavioral performance since the beginning of a trial. It relies on both direct examination of the subject and interview of informants. Unlike a targeted symptom scale, it takes into account a subject's overall functioning in the cognitive, behavioral and functional activity domains.

The ADCS-CGIC is a single value score based on a 7-point scale using the following values:

- 1 = Marked Improvement
- 2 = Moderate Improvement
- 3 = Minimal Improvement
- 4 = No Change
- 5 = Minimal Worsening
- 6 = Moderate Worsening
- 7 = Marked Worsening

Changes from baseline for ADCS-CGIC rating (1-7) will be summarized at each scheduled timepoint (Days 28, 112, and 168) (Table 14.2.7).

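### The SAP swaps the visit days for ADAS-Cog/11 and Grooved Pegboard, dropping half of the ADAS-Cog visits from its table, and plans a change from baseline for ADCS-CGIC, which has no baseline rating

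*SAP*

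**What the plan says.** SAP 5.2 states that changes from baseline in the ADAS-Cog/11 total and its 11 domain scores "will be summarized at each scheduled timepoint (Days 28, 112, and 168) (Table 14.2.2"). SAP 5.3 plans the Grooved Pegboard summaries "at each scheduled timepoint (Days 6, 28, 85, 90, 112, and 168) (Table 14.2.3").

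Two general rules in the same SAP bear on this. SAP 2.3: "All scheduled assessments after first administration of study drug will be used". SAP 2.6, on tables of change from baseline: "the baseline and post-baseline results at all planned timepoints will be included".

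The protocol sets the visits in 7.3.4 to 7.3.6. ADAS-Cog/11 is in the test lists for Visits 8 and 16, Visits 9 and 17, and Visit 19. It is also done before the infusion on the first day of the second course: "Perform ADAS-Cog/11 (Visit 11 Only"). Grooved Pegboard appears after baseline only for Visits 9 and 17 ("3. Grooved Pegboard" in that list) and Visit 19 ("4. Grooved Pegboard").

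On ADCS-CGIC, SAP 5.7 says: "Changes from baseline for ADCS-CGIC rating (1-7) will be summarized at each scheduled timepoint", namely Days 28, 112 and 168. The same section defines a 7-point scale running from marked improvement (1) through no change (4) to marked worsening (7).

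**The concern.** Each of the two SAP lists is the other instrument's protocol schedule. If the tables are programmed from the bracketed days, Table 14.2.2 leaves out ADAS-Cog results that are collected, and Table 14.2.3 makes room for Pegboard results that are not.

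The three missing ADAS-Cog days are informative ones. Days 6 and 90 are the only ADAS-Cog assessments made the day after a dosing course. Day 85 is the assessment just before the second course, 80 days after the first course ended (85 − 5). Protocol 2.2 reports that the nonclinical benefit had faded to bare significance by 3 months, so Day 85 bears on how long one course might last. None of the other seven SAP section 5 instruments is collected that day. Savonix is, but SAP 1.5 places it outside the eCRF database and section 5 plans no analysis of it.

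The omission also interacts with two other rules. The Evaluable set needs only 5 doses (SAP 2.4), and early-termination results are left out of summaries (SAP 5). A subject who attends every visit to Day 90 and leaves before Day 112 would contribute only Day 28 to the ADAS-Cog table, despite scheduled values on Days 6, 85 and 90.

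The ADCS-CGIC problem is separate. A change from baseline needs a baseline rating to subtract, and a baseline covariate needs one to enter. If neither exists, SAP 5.7 does not say what is tabulated or which null value applies.

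**Working it through.** **1. Visit lists side by side.** Protocol days come from 7.3.4 to 7.3.6, using Visit 8 = Day 6, 9 = 28, 10 = 56, 11 = 85, 16 = 90, 17 = 112, 18 = 140 and 19 = 168. SAP days come from 5.1 to 5.8.

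| Instrument | Protocol, post-baseline days | SAP days | Omitted by SAP | Listed, no data |
|---|---|---|---|---|
| MMSE | 6, 90, 168 | 6, 90, 168 | none | none |
| ADAS-Cog/11 | 6, 28, 85, 90, 112, 168 | 28, 112, 168 | 6, 85, 90 | none |
| Grooved Pegboard | 28, 112, 168 | 6, 28, 85, 90, 112, 168 | none | 6, 85, 90 |
| CFT | 28, 112, 168 | 28, 112, 168 | none | none |
| CDR-SOB | 28, 112, 168 | 28, 112, 168 | none | none |
| ADCS-ADL23 | 28, 56, 112, 140, 168 | same | none | none |
| ADCS-CGIC | 28, 112, 168 | 28, 112, 168 | none | none |
| NPI-Q | 28, 56, 112, 140, 168 | same | none | none |

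Six of eight lists match. In the other two, the SAP's ADAS-Cog list equals the protocol's Pegboard list and the reverse, exactly. The Schedule of Events (protocol section 17) agrees on the counts: seven ADAS-Cog marks and four Pegboard marks, each including baseline.

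**2. Size of the ADAS-Cog omission.** 3 of 6 post-baseline visits = 50%. The table carries 12 scores (total plus 11 domains), so 12 × 3 = 36 of 12 × 6 = 72 score-by-visit summaries are missing, in both the Evaluable and the Per Protocol versions. The second count is the same 50% expressed in table cells, not further evidence.

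**3. Timing, on nominal days.** Courses end on Days 5 and 89.

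- First tabulated value after a course, SAP as written: 28 − 5 = 23 days and 112 − 89 = 23 days.
- With the protocol's visits: 6 − 5 = 1 day and 90 − 89 = 1 day.
- Gap in the table across the second course: 112 − 28 = 84 days.
- Late follow-up is kept: 168 − 89 = 79 days after the last infusion.

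Visits 9, 11 and 17 each have a ±7-day window, so actual intervals vary around the 23 and 84 days.

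**4. ADCS-CGIC.**

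- Protocol 7.1.1.3.7 describes the score as the clinician's view of change since the start of the trial.
- Appendix 5 makes the baseline part a record of notes for later reference. The 7-point judgement follows the interviews at follow-up visits, and the appendix says it rates change rather than severity.
- The number of baseline ratings scheduled on the 1 to 7 scale is therefore 0, although Visit 2 lists the instrument.
- SAP 2.6 requires baseline results in every change table. SAP 5 allows a paired t-test for each efficacy endpoint, looks at changes around zero, and allows an ANCOVA with baseline as covariate. None of these can be applied to a score without a baseline.
- If the rating itself were put in place of the change, zero would still be the wrong null: the scale starts at 1, and no change is 4.

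**The case against.** The strongest defence is that the SAP does not decide to drop visits. Sections 5.2 and 5.3 refer to each scheduled timepoint, with the days only in brackets; SAP 2.3 and 2.6 require all scheduled visits; and SAP 1 says to read the SAP with the protocol. The mock shells are a separate document, not available here, and may be right. Empty Pegboard columns would probably expose the error at the first run, and SAP section 10 lets tables be modified with the sponsor's approval. All of this is fair, but it shows that the SAP contradicts itself, not which statement governs. The bracketed days are the explicit instruction to a programmer. SAP section 8, which lists changes from the protocol, does not mention these days.

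A second point stands in part. Even the corrected table gives only mean changes from study baseline at Days 85 and 90, not a paired Day 85 to Day 90 change with its SD. Restoring those days lets a reader see the level on either side of the second course; it does not by itself supply a paired analysis.

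On ADCS-CGIC, the appendices are labelled as examples, with actual scoring in a Rater Reference Manual that is not available here, and the SAP 5.7 wording may be loose phrasing for summarising the rating. The section 5 tests are also optional. Loose phrasing is plausible. But the main protocol text and the SAP's own scale already make the score a rating of change, so the conclusion does not depend on the appendix alone.

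Finally, the study is not powered for cognition and these endpoints are mainly descriptive. That limits the importance of the point, not its correctness.

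**Conclusion.** The concern holds. The SAP's ADAS-Cog/11 and Grooved Pegboard day lists are the reverse of the protocol's. As written, Table 14.2.2 omits 3 of 6 post-baseline ADAS-Cog visits and Table 14.2.3 lists 3 of 6 Pegboard visits that have no data. SAP 5.7 asks for a change from a rating that is not made at baseline, at all 3 of its visits.

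That the lists were exchanged by mistake is an inference, strongly supported by the exact two-way match and the six correct lists. The effect on the tables assumes that the bracketed days are followed. The ADCS-CGIC conclusion assumes that the instrument is scored as the protocol describes.

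This should be corrected before database lock, but it is limited in reach. The primary safety, tolerability and feasibility results, the sample size and the error rates do not change, and Listing 16.2.6.2 shows all ADAS-Cog data in either case.

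**What to change.** Before database lock:

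- In SAP 5.2, list Days 6, 28, 85, 90, 112 and 168.
- In SAP 5.3, list Days 28, 112 and 168.
- In SAP 5.7, replace the change from baseline with a summary of the rating itself at Days 28, 112 and 168, as counts and percentages per category, a form that protocol 10.4.1 already provides for categorical endpoints.
- State that any optional within-group test of ADCS-CGIC uses 4 as the null, and that any between-group comparison omits the ADCS-CGIC baseline covariate. The choice of test can stay within the methods in protocol 10.4.1.
- Check the mock shells for Tables 14.2.2, 14.2.3 and 14.2.7 against the corrected text.

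With the lists exchanged, ADAS-Cog covers 6 of 6 visits and Pegboard 3 of 3, with none omitted and none empty. The cost is SAP wording and, if they carry the same days, the table shells. No new visit, assessment or data collection is needed.
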